Study Protocol and Statistical Analysis Plan

Evaluating Benefits of Hearing Aid Microphone Directionality Technologies

V.2

May 24, 2022

NCT04953390

Protocol Title

Evaluating Benefits of Hearing Aid Microphone Directionality Technology

1 Background

Paradise hearing instruments (HI) have an adaptive binaural beamformer, known as Stereozoom (SZ) that is activated in speech in loud noise (SiLN) environments. SZ has been proven to provide speech intelligibility (SI) benefits to HI users in noise. In particular, SZ has shown up to a 5.5 dB improvement over an omnidirectional microphone and up to 1.5 dB improvement over Phonak's monaural beamformer, Ultrazoom (UZ), in speech reception threshold (SRT) assessments in noise. A summary of these findings can be found in the "Phonak Compendium Stereozoom Part I: the benefit of wirelessly connected narrow directionality in Phonak hearing aids for speech intelligibility" by Stewart et. al (2019) available on phonakpro.com. SZ achieves these speech intelligibility benefits through mixing the input of each hearing instrument (HI) to create a narrow beam with a variable null that adapts in accordance to the noise source(s).

The effect of this mixing is a narrow beamformer with a high directivity index (DI) that is ideal for listening to single, front-facing speech sources. However, the mixing of HI inputs also results in the loss of spatial perception.

In comparison, the monaural beamformer, Ultrazoom (UZ), does not mix the HI inputs between sides. As such, it retains localization cues and; therefore, creates a spatial release from masking.

Accordingly, there is a tradeoff between Stereozoom and Ultrazoom, wherein SZ provides better directivity and UZ provides better spatial awareness. Good directivity and spatial awareness both contribute to improved speech intelligibility, so it is problematic to have to choose between one or the other.

Therefore, there is an opportunity to balance the advantages of both to optimize the performance of the binaural beamformer. This might be achieved through a change in the binaural beamformer strength. Today, in Paradise devices, the beamformer strength of SZ can be thought of as 70%. As such, the opportunity to change the beamformer strength could mean making the beamformer wider (<70%) or narrower (>70%), and both should be explored. In addition to the binaural beamformer strength, it would also be worthwhile to investigate the transition speed for binaural beamformer activation. The current transition speed for SZ is instantaneous (time constant = 0 sec.), which may be disturbing for some users. Elongating the transition time may result in a more pleasant user experience.

StereoZoom 2.0 is a new parameterization that balances the tradeoff between UZ and SZ. It has not yet been evaluated on human subjects. An evaluation of this feature with human subjects may identify which beamformer strength and transition speed settings strike the best balance between good directivity and spatial awareness while maintaining a pleasant user experience.

2 Objectives

The primary objective is to investigate the effect of binaural beamformer strength on spatial perception in speech in noise (SiN) environments through a subjective spatial awareness task comparing three beamformer strengths, including Stereozoom (SZ), with experienced hearing aid users with moderate hearing loss.

List of the secondary objectives:

- a. The secondary objective is to investigate the effect of binaural beamformer strength on speech intelligibility in noise through an objective SRT task comparing three beamformer strengths, including SZ, with experienced hearing aid users with moderate hearing loss.
- b. The secondary objective is to investigate the perceived benefit(s) of user steering of the binaural beamformer strength for SiN with experienced hearing aid users with moderate hearing loss.
- c. The secondary objective is to investigate the perceived benefit(s) of longer transition time (> 0 sec) for activation of the binaural beamformer through a comparison of multiple transition times with one beamformer strength, with experienced hearing aid users with moderate hearing loss.

3 Description of the investigational device

This clinical investigation is intended to further development of the StereoZoom 2.0 feature. This feature will be available in future iterations of the Phonak Audeo hearing devices. The overall intended purpose of the device is to amplify and transmit sound to the ear and hereby compensate for impaired hearing.

4 Design of the clinical investigation

This interventional study will have 2-3 conditions per task for a sample population of 15-20 human subjects. The order of conditions will be counterbalanced and the participants will be blinded to the conditions.

5 Risks and benefits of the investigational device and clinical Investigation

There are minimal risks associated with both the investigational device and participating in the clinical investigation. The device used presents non-significant risk per FDA. The benefits of participating in the investigation include the benefit of personal satisfaction for participating in research to improve hearing instrument technology. Additionally, subjects will also be compensated for their time in participating in this study.

6 Endpoints

Primary endpoint: Subjective ratings of the beamformer strength conditions

- Subjective outcome parameters: 1) Perception of beamformer strength via a 100pt scale of 5pt increments from wide to narrow (0 = wide, 100 = narrow) and 2) Preference of beamformer strength via a 100pt scale of 5pt increments from not preferred to preferred (0 = not preferred, 100 = preferred).

Secondary endpoint: Objective and subjective measures

- Matrix Test outcome parameter: SRT 50%

- User steering of beamformer via a slider in a mobile app outcome parameter: subjectively perceived benefits measured via the grouping of the beamformer setting the user chose alongside their response to two questions:

1) Did you notice a change when moving the slider? (No difference, slight difference, clear difference)

2) Are you satisfied with what you could achieve with the slider? (Not satisfied, somewhat satisfied, definitely satisfied)

- Headphone recordings outcome parameter: Noticeability of beamformer transition in A/B comparisons comprised of 4 transition speeds.

7 Inclusion and Exclusion Criteria

Subjects fulfilling all of the following inclusion criteria are eligible for the investigation:

- 18-90 years of age
- Moderate to moderately severe (N3-N4) bilateral sensorineural hearing loss
- Fluent in English; ability to read and write in English
- Willing and able to provide informed consent
- Participants must be experienced hearing aid users with symmetrical hearing loss defined as a difference of ≤ 10 dB between ears an air bone gaps ≤ 10 dB.
- Must be able to use app and smart phone.

The presence of any one of the following exclusion criteria will lead to the exclusion of the subject:

- Self-reported ear-related pathology (otorrhea w/in 90 days, dizziness, sudden hearing loss or worsening of hearing w/in 90 days, otalgia)
- Visible deformity of the ear
- Chronic, severe tinnitus
- Unilateral hearing loss
- Cognitive impairment
- Asymmetrical hearing loss
- Other diagnoses that may cause fluctuations in hearing (i.e. Meniere's)
- Unable to tolerate the physical fit of a RIC device
- Visual impairment that prevents the participant from seeing the adjustment slider in the mobile app
- Inability to be seen for 3 lab visits

8 Measurements and procedures

All home-trial data is locally stored on the participant's phone and will be manually extracted via a wired connection during their lab visits after each two week home trial. The extracted data is then saved in a company network drive.

All lab data is collected digitally. There are no paper questionnaires or result sheets in this investigation. The data files are saved in a company network drive after task completion.

All analysis of the results will occur at the conclusion of the study.

9 Statistical design and analysis

A priori sample size estimation was not performed for this investigation, as the investigation is exploratory and does not aim to confirm any effect with statistical significance and power.

This is an exploratory trial and will not have statistical criteria for termination.

Speech recognition thresholds will be recorded in dB SPL. SRT results will be recorded along with the anonymous participant ID, and task condition. Qualitative data will be collected as a question, response, and anonymous participant ID.

Analysis of the qualitative data will take place at the conclusion of the trial. Data (raw or trans-formed, per above) will be subjected to analysis via linear mixed effects modeling. The model will be constructed to regress (raw or transformed) subjective rating on a dummy variable of condition (fixed effect). This model will allow the investigators to evaluate the relative difference in subjective ratings between the beamformer strengths.

Analysis of the SRT data and qualitative data related to the secondary objectives will take place at the conclusion of the trial, using similar methodology at described above.

10 Investigation Duration

Expected duration of each participant's participation is 4-5 weeks.

11 Data Handling and Management

Study data is recorded both with paper and with electronic Case Report Forms (p/eCRF). For each enrolled study participant a CRF is maintained. All CRFs are kept current to reflect the subject's status at each phase during the course of study. Participants cannot be identified in the CRF by name or initials and birth date but an appropriate coded identification is used. All study team members are authorized for the CRF entries and it is assured that any authorized person can be identified both for pCRFs and eCRFs. If pCRFs are used, the investigator's acronym as well as the subject ID is filled in and data are entered into an electronic file for analysis by the respective investigator and data get monitored by the assigned monitor. In case of a self-evident corrections, either the subject does it by himself or the investigator undertakes the correction by crossing out the word/sentence with a single horizontal line and by adding the correction including his personal identifier and the date.

Source documents for this investigation include, audiograms, Target fitting files, appointment checklists, data packages extracted from the app, and digital results packages exported from software used to collect data from lab tasks.

Any paper-based data will be stored in a locked filing cabinet at the investigation site. All electronic data will be stored on an access-restricted server owned, operated, and maintained by Sonova USA. Servers used to store data in this investigation are physically located in the US. Permission to access data will be limited to study manager, monitor, PI, and essential research staff, as designated by the principal investigator.

During data collection of the investigation, physical copies of the data will be compiled and digitized by the study manager on a daily basis. Data will be reviewed for misentries or inaccuracies as each data set is entered.

The extent and nature of monitoring appropriate for the clinical investigation including the strategy for source data verification (SDV) are based on considerations such as the objective, design, complexity, size critical data points and endpoints of the clinical investigation. A de-tailed plan for monitoring arrangements is provided separately from this CIP.

12 Amendments to the CIP

If it is necessary to make an amendment to this CIP, the changes to the CIP will be clearly identified with the date the change was made, and the version number will be incremented. Non-substantial amendments (e.g., correcting a typographical error) will be recorded as a mi-

nor version incrementation, whereas substantial amendments (e.g., a change to the study procedure or statistical plan) will be recorded as a major version incrementation. In an emergency situation, this CIP will be amended and updated only after participant health and safety have been assured and FDA/WIRB have been notified (as applicable).

13 Deviations from clinical investigation plan

Deviations from the CIP to protect the rights, safety and well-being of human participants under emergency circumstances may proceed without prior approval of the sponsor and the EC – such deviations will be documented and reported to the sponsor representative (Study Manager) and the EC as soon as possible. Apart from that the investigator is not allowed to deviate from this CIP unless that deviation does not influence the investigation data.

14 Device accountability

The PI or authorized designee keep records documenting the following in a written process:

- Names of participants who received, used, returned, or disposed of device
- Date of receipt, identification, and quantity of each investigational device (batch/serial number or unique code)

Expiry date (if applicable)

- Date(s) of use

15 Informed consent process

Informed consent will be obtained from participants prior to any study participation in accordance with the IRB guidelines. The participants will be granted sufficient time to read through the consent in full and ask any questions they have before signing. After the participant signs the consent form, the researcher will sign and provide a copy to the participant. This process will take place in a private office located in the Phonak Audiology Research Center (PARC). Participants will be incentivized with a monetary stipend of 30 USD per hour spent at the investigation site, plus mileage reimbursement for round-trip travel between the investigation site and their home address. Mileage reimbursement will be calculated based on the shortest driving distance in miles multiplied by the Internal Revenue Service's (IRS) standard mileage rate at the time the study concludes.

Informed Consent will only be obtained by investigation participants who can provide informed consent themselves before enrollment.

16 Adverse events, adverse device effects and device deficiencies

Device deficiencies and all **adverse events (AE)** including all **serious adverse events (SAE)** are collected, fully investigated and documented in the source document and appropriate case report form (CRF) during the entire investigation period, i.e. from participant's informed con-sent until the last protocol-specific procedure, including a safety follow-up period (ISO-14155, 2020). Documentation includes dates of event, treatment, resolution, assessment of serious-ness and causal relationship to device and/or investigation procedure.

Information on AEs is systematically collected during the regular investigation visits, and phone calls (if applicable).

The investigator(s) will follow-up on a biweekly basis with any participant experiencing an AE until either a) the participant reports resolution of the AE or b) 8 weeks have passed since the participant's final visit. If, however, the participant's condition worsens throughout the 8

week follow-up period, the investigator will continue to follow-up biweekly until the AE is resolved or the participant's condition stabilizes over an 8 week period.

The causality assessment of the SAE will be conducted according to MDCG 2020-10/1 Safety Reporting in Clinical Investigations of Medical Devices under Regulation (EU) 2017/745.

The reporting of Serious Adverse Events and Device Deficiencies follows the Regulation (EU) 2017/745 and the MDCG 2020-10/1 Safety Reporting in Clinical Investigations of Medical Devices under Regulation (EU) 2017/745.

17 Vulnerable Populations

This investigation will not include any vulnerable populations.

18 Suspension or premature termination of the clinical investigation

The study will be terminated if the majority of the participants are not able to wear the devices for the study visit.

The study will be terminated if the participants or researchers are exposed to safety risks other than those outlined in this document.

The study may be terminated in the event natural disasters, widespread outbreak of illness, compromised structure of the investigation site, etc. that would make continuation of the study impossible or impractical. The study will be suspended within 5 days of determination that the study or device put participants at an unreasonable risk.

If a participant is suspended, terminated, or withdraws from the study, their data can be traced with their unique study identification number.

According to the FDA, follow-up is required for participants who experience Serious Adverse Events. Follow up will be conducted by the study manager and/or the PI until the nature of the event is resolved.

19 Publication policy

The clinical investigation will be registered in clinicaltrials.gov, a publicly accessible database, as required by U.S. regulations.

The results of the clinical investigation will be published on clinicaltrials.gov no later than one calendar year following the final participant appointment.

An internal report of the results of this investigation will be completed and uploaded to eQMS.

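### Objective (c) asks about the perceived benefit of a longer transition, but the only outcome specified for it is noticeability, and the plan does not say how noticeability is to be read as benefit

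*Combined protocol and SAP*

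**What the plan says.** Section 2, objective (c), is to "investigate the perceived benefit(s) of longer transition time (> 0 sec) for activation of the binaural beamformer", by comparing several transition times at one beamformer strength. Section 1 says what the benefit would be. The current switch is instantaneous, "which may be disturbing for some users", and "Elongating the transition time may result in a more pleasant user experience". Section 1 also expects an evaluation in people to show "which beamformer strength and transition speed settings strike the best balance between good directivity and spatial awareness while maintaining a pleasant user experience".

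Section 6 gives one outcome for transition time: "Headphone recordings outcome parameter: Noticeability of beamformer transition in A/B comparisons comprised of 4 transition speeds".

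Two other tasks in Section 6 do collect a judgement of liking. Beamformer strength has "Preference of beamformer strength via a 100pt scale of 5pt increments from not preferred to preferred", next to a separate rating of perceived width. The slider task has "subjectively perceived benefits measured via the grouping of the beamformer setting the user chose alongside their response to two questions": one asks whether a change was noticed, the other is "Are you satisfied with what you could achieve with the slider".

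Section 9 fits a linear mixed model of subjective rating on condition for the ratings and says the secondary data will be handled in much the same way. It names no variable for transition time.

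**The concern.** Noticing a transition and preferring it are different responses. A participant may hear the switch and not mind it, or hear a slower one less clearly and still prefer the fast one. The reason given for lengthening the transition is comfort, yet the task records detection.

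At stake is the conclusion that objective (c) can support. If the speeds differ in noticeability, the report could describe that difference. To call it a benefit, it would have to assume that less noticeable means better, which the plan neither states nor tests. A response that was not collected in the sessions cannot be recovered in the analysis.

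**Working it through.** The plan has no figure of its own to reproduce: Section 9 says no sample size was calculated. The check is a comparison of passages, followed by arithmetic on what the remedy would deliver.

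**1. Objective against outcomes.** Section 6 lists five outcome measures.

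| Outcome (Section 6) | Detection or perception | Liking or satisfaction |
|---|---|---|
| Strength: perceived width | yes | no |
| Strength: preference | no | yes |
| SRT 50% | performance measure | no |
| Slider: setting plus two questions | yes (noticed a change) | yes (satisfied) |
| Transition: A/B noticeability | yes | no |

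One of the five concerns transition time, and it records detection. Evaluative items number 1 of 2 ratings for strength, 1 of 2 questions for the slider and 0 of 1 for transition.

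**2. Does another section fill the gap?** Section 8 covers storage and extraction of data, not the content of the tasks. Section 9 says that qualitative data are held as a question, a response and a participant ID, and specifies no further item. Its model needs a rating as input, so it cannot supply one.

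**3. The reference setting.** Objective (c) is about times above 0 sec, so benefit has to be judged against 0 sec. Section 6 does not say that 0 sec is one of the 4 speeds. If it is, all-pairs testing gives 4 × 3 / 2 = 6 pairs, of which 3 compare a longer time with 0 sec. Section 4 also speaks of 2-3 conditions per task. That agrees with 4 speeds only if each A/B pair counts as a two-condition task, so the two sections should be reconciled.

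**4. What one added item would estimate.** For one pair, let L, S and N be the numbers choosing longer, shorter and no preference, with n = L + S + N participants. The contrast is d = (L − S)/n, and 0 means no net preference.

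- If N = 0, then d = 2p − 1 with p = L/n, so a 95% Wilson interval for p converts directly:

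| L of n | p (95% Wilson) | d in points (95%) |
|---|---|---|
| 8 of 15 | 53% (30 to 75) | 7 (−40 to 50) |
| 12 of 15 | 80% (55 to 93) | 60 (10 to 86) |
| 10 of 20 | 50% (30 to 70) | 0 (−40 to 40) |
| 16 of 20 | 80% (58 to 92) | 60 (17 to 84) |

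- If N > 0, the simple large-sample standard error is √[(L + S) − (L − S)²/n] / n. Take L = 6, S = 2, N = 7, n = 15 as an illustration. Then d = 4/15 = 27 points, SE = √(8 − 16/15)/15 = 0.176, and the interval is 27 ± 34, or −8 to 61. The score interval for a paired difference gives −11 to 57.
- In that illustration the share choosing longer among all participants is 6/15 = 40%. This is below half although longer is favoured 3 to 1, which is why the contrast is the better summary.
- The simple interval fails at this sample size when preferences are lopsided. For 12 against 3 of 15 it is 60 ± 40.5, with an upper limit above 100. The score interval avoids this.

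**5. Burden.** The number of pairs is not given. Assuming 3 to 6 pairs, one or two orders and 10 to 20 s per response: 3 × 1 × 10 = 30 s, up to 6 × 2 × 20 = 240 s.

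**The case against.** The strongest reply is that the stated problem is disturbance, and a transition that a listener does not notice can hardly disturb that listener. The slider task even counts a noticing question among its measures of perceived benefit. This stands in part: noticeability is relevant to objective (c). A reader might infer that the outcome says nothing about benefit, and the documents do not support that. The slider parallel is weaker than it looks, because noticing a change is wanted there and probably unwanted here, and there it is paired with a satisfaction question. The plan does not state the link from noticeability to benefit or its direction.

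A second reply is that the document is brief. The wording of the A/B question is not given, so a preference question may be asked in practice. This also stands as a limit. The documents show that no such response is specified, not that none will ever be collected. But Section 6 writes out both slider questions, and for transition time it lists noticeability alone.

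A third reply is that the study is exploratory and aims to confirm nothing. That explains the absence of a power calculation. It does not make an outcome fit an objective that it does not measure, though it does lower the importance of the point.

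Finally, the plan already has a 0-100 preference scale and a model for ratings, and that scale could be used for each speed instead of a pairwise choice. This is a reasonable alternative. A choice within the existing comparisons is suggested because it adds one response and no new listening.

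**Conclusion.** The mismatch is real and confined to objective (c). As specified, the trial can describe how noticeable the speeds are, but it has no response showing whether participants find a longer transition better, and no rule for reading noticeability as benefit. No numerical error or bias in a planned estimate is claimed: the quantity of interest is simply not specified for collection.

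A reader might go further and infer that the transition task is worthless or that the trial's main conclusion is at risk. Neither follows. Noticeability is informative in its own right, and the primary endpoint has its own preference rating.

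Importance is low to moderate. The conclusion assumes that Section 6 is the full list of outcomes and that perceived benefit means what Section 1 describes: less disturbance and a more pleasant experience.

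**What to change.** **Section 6.** After the noticeability response in each existing A/B comparison, add one evaluative response, for example: *Which is more pleasant: A, B, or no preference?* Make it the outcome for objective (c) and keep noticeability as supporting. State whether 0 sec is one of the 4 speeds. Base the answer to (c) on the pairs that set a longer time against 0 sec. If 0 sec is not included, say that the item only ranks longer times against each other.

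**Section 9.** For each pair, report the counts choosing longer, shorter and no preference, with the participant as the unit. Give the longer-minus-shorter difference in proportions with a 95% interval, preferably a score interval at this sample size, so that 0 is the no-benefit benchmark. State that this takes the place of the mixed model for this item. If pairs are played in both orders, use one result per participant and report discordant answers separately from no preference.

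**Cost.** One response per comparison, about 0.5 to 4 minutes per participant under the assumptions above, plus a few sentences in the plan. The pleasantness question may colour later noticeability answers; asking noticeability first in each comparison limits this but does not remove it.

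**Fallback.** If the item cannot be added, limit objective (c) and its conclusion to noticeability. This costs no session time but gives up the benefit question.

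### Condition order is counterbalanced but the model has no position term, so any order effect inflates the residual and makes the intervals for the condition contrasts too wide

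*Combined protocol and SAP*

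**What the plan says.** Section 4 gives the design: "This interventional study will have 2-3 conditions per task for a sample population of 15-20 human subjects". It adds: "The order of conditions will be counterbalanced and the participants will be blinded to the conditions". The counterbalancing scheme is not described. Section 2 makes the comparison of three beamformer strengths the primary objective.

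Section 9 specifies a linear mixed effects model for the ratings: "The model will be constructed to regress (raw or transformed) subjective rating on a dummy variable of condition (fixed effect". No other fixed effect is named, and no random effect is given. The SRT and the other secondary data are to be analysed "using similar methodology at described above". No term for position, period or sequence appears anywhere in the document.

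Section 9 also describes the study as exploratory, with no sample size calculation.

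**The concern.** Counterbalancing makes presentation position a design factor. It stops a position effect from leaning on one condition more than another, but it does not take that effect out of the data. A model with participant and condition only has nowhere to put a systematic shift from first to third position except the residual. The condition contrast is then exactly as precise as before, but it is reported as less precise.

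This matters because the primary question is a within-person comparison of three settings in 15-20 people. An exploratory study of this size is useful mainly for its estimates and the uncertainty attached to them. Intervals that are wider than the data justify could hide a difference that would help in choosing a setting.

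A second consequence depends on the final sample size. If participants do not divide evenly over the orders, part of the position effect does enter the condition contrast as bias.

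**Working it through.** The plan states no SE, power or SD, so there is no figure of its own to reproduce.

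**Inputs from the documents:** three strengths (section 2); 15-20 participants and counterbalanced order (section 4); condition as the only named fixed effect (section 9).

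**Assumptions:** a participant intercept is in the model; one rating per condition per participant; a linear shift d per position, common to all participants; within-person residual SD s; two-sided 95% t intervals.

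**1. Inflation of the SE under exact balance**

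The centred position effects are -d, 0 and d, with sum of squares 2d². Left out of the model, they add n × 2d² to a residual sum of squares with 2(n-1) degrees of freedom. Hence:

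- expected residual mean square = s² + d² × n/(n-1)
- reported SE / true SE = sqrt(1 + (n/(n-1)) × (d/s)²)

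At n=18, n/(n-1) = 18/17 = 1.0588. The drift column takes s=15 points for illustration. The last two columns come from 20,000 simulated trials (six orders, three participants each) with a true difference of 14.4 points, which the model with position detects about 80% of the time.

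| d/s | Drift, first to third position (2d) | SE ratio | Coverage of nominal 95% CI, no position term | CI excludes zero, no position term |
|---|---|---|---|---|
| 0 | 0 points | 1.000 | nominal | about 80% |
| 0.25 | 7.5 points | sqrt(1.066) = 1.033 | 95.4% | 78% |
| 0.5 | 15 points | sqrt(1.265) = 1.125 | 97.1% | 73% |
| 1.0 | 30 points | sqrt(2.059) = 1.435 | 99.5% | 49% |

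The formula depends little on n: at d/s=1.0 it gives 1.44 at n=15 and 1.43 at n=20.

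**2. The true precision does not change**

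The true SE is s × sqrt(2/n) = 15 × sqrt(2/18) = 5.00. In the simulation at d/s=0.5, the SD of the estimate was 5.03 under both models. The mean reported SE was 5.58 without position and 4.95 with it. At d/s=1.0 the SD was 4.96 under both, and the reported SEs were 7.14 and 4.97. At d/s=0 both reported SEs were 4.96. A separate simulation of 4,000 runs per setting gave the same SE ratios within simulation error, and coverage of 94.4% to 95.2% at n=18 once position was included.

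**3. Bias when the orders do not balance**

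Bias = d × (mean position of condition A minus mean position of condition B). Over the six possible orders, A's position minus B's is -1, -2, +1, +2, -1, +1, which sums to zero. Only leftover participants contribute. Taking the least favourable set of distinct leftover orders:

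| n | Leftover | Worst-case bias |
|---|---|---|
| 15 | 3 | (2+1+1)d/15 = 0.267d |
| 16 | 4 | (2+1+1-1)d/16 = 0.188d |
| 17 | 5 | 2d/17 = 0.118d |
| 18 | 0 | 0 |
| 19 | 1 | 2d/19 = 0.105d |
| 20 | 2 | (2+1)d/20 = 0.150d |

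With a three-order Latin square the differences are -1, +2, -1. The bias is zero at n=15 and n=18 and at most 2d/16 = 0.125d otherwise.

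**4. Cost of the position term**

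At n=18 the residual degrees of freedom fall from 34 to 32 and the t critical value rises from 2.0322 to 2.0369, or 0.2%. At n=15 the rise is 0.35%.

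**The case against.** The strongest reply is that nothing here makes the estimates wrong. Counterbalancing is the design's protection against order effects. Under exact balance the contrast is unbiased, and the error in the SE is on the cautious side. The whole effect depends on a drift that the documents do not mention. At 7.5 points from first to third position it is 3%, and only a 30-point drift gives 43%. All of this stands, so the 43% and 49% figures should be read as an outer limit.

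The inflation also shrinks under other readings of the design. At n=18 and d/s of 0.25, 0.5 and 1.0, it is about 2.5%, 10% and 35% with two ratings per condition taken in the same position, and about 1.6%, 6% and 24% for a task with two conditions. The documents do not give the number of ratings.

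The study disclaims significance and power, and section 9 names no confidence interval or test. The detection percentages therefore only illustrate what wider intervals mean. That intervals matter here is an inference from the exploratory aim.

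The bias from imbalance is small: at n=15, s=15 and d/s=0.25 (d=3.75) it is at most 0.267 × 3.75 = 1.0 point, against a contrast SE of about 5.5 and a scale with 5-point steps.

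A position term corrects only an additive shift common to all participants. It does not remove carryover or drift that differs between people.

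Finally, a one-sentence model description does not forbid a position term. That is true, but an analyst who follows the plan as written would fit condition alone. These points limit the size of the problem without removing it.

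**Conclusion.** The concern holds. The plan controls order in the design and leaves it out of the stated model, so any additive position effect inflates the reported SE of every condition contrast. For three conditions, one rating each and n=18, the overstatement is 0% with no drift, 3% at d/s=0.25 and 12% at d/s=0.5, with 43% as an extreme. If the orders are unbalanced there is also a bias of at most 0.27d. The direction and the formula are firm. The size is not, because d, s, the number of ratings and the counterbalancing scheme are all unstated. The consequence is needlessly wide intervals in an exploratory study, not a false positive finding. The change is worth making because it is nearly free and does practically no harm if there is no order effect.

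**What to change.** In section 9, state that the ratings, and likewise the SRT, are modelled on condition and presentation position (both categorical) with a participant random intercept. Treating position as categorical avoids assuming a linear drift. Naming the random intercept also supplies the random term that the plan leaves unstated.

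Add that condition and position are kept with every rating and every SRT. Section 9 lists participant ID and task condition for the SRT, and position may already be in the "digital results packages exported from software used to collect data from lab tasks" that section 11 counts as source documents, so this needs only a check of the export fields.

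The cost is one or two sentences, that check and a new major version, since section 12 says that "substantial amendments (e.g., a change to the study procedure or statistical plan) will be recorded as a major version incrementation". Statistically it uses two residual degrees of freedom, as shown above. No visit, procedure or sample size changes.
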